5.0 GUIDANCE FOR REMOTE SUBJECT VISITS

Potential disruptions to the study may be necessary due to current or future pandemic-related emergency restrictions. Possible disruption of the study as a result of COVID-19 control measures may lead to delays in scheduled follow-up visits.

Subjects may be delayed in being seen for study follow up visit(s), for example due to COVID-19 control measures or due to the subject's concerns or fears about COVID-19 risk. When appropriate, the remote assessment will be conducted to the extent possible. Discussions with the subject during remote assessments may include:

Title:	Guidelines for COVID-19 Risk Mitigation	
Document Type:	Work Instruction	
Document Number:	VWI-0081	Revision Number: 1

Procedure	Details
Subject Reported Ocular Symptoms	Subjects will respond to a verbal open-ended symptoms questionnaire regarding the test article when applicable and feasible.
Change of Medical History (Adverse Events) and Concomitant Medications / Therapies Review	Record any adverse events or medical history changes from the previous study visit with the subject/parents. Review the subject's concomitant medications/therapies and record any changes from the previous study visit.
Wearing Time and Compliance	Record the average wearing time (including number of hours per day during weekdays and weekends, and number of days per week). Confirm compliance with the prescribed wear schedule. • Record and discuss the lens wear compliance based on the subject's self-report. For example, the subjects will be asked the time of the day the subject typically puts on the study lenses in the morning and takes off in the evening, the number of days per week lenses were worn, and the number of consecutive days the subject didn't wear the study lenses, etc.

The discussion with the subject will be documented in EDC under Tele-Visit and a minor protocol deviation will be noted. If during the telephone consultation, a subject states he/she wishes to discontinue participating in the study, instruct the subject to stop wearing the study lenses and schedule the subject to return to the clinic for a Final Evaluation at the earliest possible time. Subjects should return all unused lenses to the clinic at the last visit.

Changes in study visit schedules, missed visits, or participant discontinuations may lead to missing data, including data related to protocol-specified procedures. Case report forms should capture specific information regarding the basis of missing data, including the relationship to the COVID-19 pandemic.

6.0 STUDY CONDUCT DURING PANDEMIC

It is recognized that the Coronavirus Disease 2019 (COVID-19) pandemic may have an impact on the conduct of this clinical study due to, for example, self-isolation/quarantine by participants and study-site personnel; travel restrictions/limited access to public places, including Optometry Clinics; and changes in clinic procedures required to address the COVID-19 challenge.

Every effort should be made to adhere to protocol-specified assessments for study participants, including follow-up. However, if scheduled visits cannot be conducted in person at the study site it is suggested that assessments be performed to the extent possible remotely/virtually or delayed until such time that on-site visits can be resumed in order to continue participant monitoring in accordance with the protocol where possible. At each contact, participants will be interviewed to collect safety data. Key efficacy endpoint assessments should be performed if required and as feasible.

Modifications to protocol-required assessments may be permitted via COVID-19 Appendix after consultation with the participant, investigator, and the sponsor. Missed assessments/visits will be captured in the clinical trial management system for protocol deviations. Interruptions of test article wear or discontinuations of study interventions and withdrawal from the study should be documented with the prefix "COVID-19-related" in the case report form (CRF).

Title:	Guidelines for COVID-19 Risk Mitigation
Document Type:	Work Instruction
Document Number:	VWI-0081

The sponsor will continue to monitor the conduct and progress of the clinical study, and any changes will be communicated to the sites and to the health authorities according to local guidance.

If a participant has tested positive for COVID-19, the investigator should contact the sponsor's responsible medical monitor to discuss initial plans for study intervention and follow-up. The medical monitor will notify the Safety Management Team of any subject(s) that have reported "COVID-19", "Asymptomatic COVID-19", or "Suspected COVID-19" adverse events within 24 hours of the notification.

Modifications made to the study conduct as a result of the COVID-19 pandemic will be summarized in the clinical study report.

COVID-19 screening procedures that may be mandated by local healthcare systems do not need to be reported as an amendment to the protocol even if done during clinical study visits.

6.1 Monitoring Visits

When on-site monitoring by the sponsor is not feasible, the sponsor's site monitor will contact the study site to schedule remote visits. In such cases, on-site monitoring visits will resume when feasible, with increased frequency to address the source data verification backlog.

Even with staffing limitations during this COVID-19 pandemic, all routine operations related to clinical trials should be well-documented and archived as part of standard process. When conditions permit, all parties involved in this clinical trial should communicate relevant information in a timely manner so that all relevant parties remain sufficiently informed.

6.1.1 Study Site Initiation:

During the period that this Work Instruction is in effect, Site Initiation Meetings and training of study site staff will be conducted remotely. The JJVCI study team will conduct training via Skype, Zoom, Microsoft Teams or similar software as well as utilize online training materials, as applicable. Study site training will be documented utilizing Site Initiation Report (Form Control No. **VCT-0063**) per Study Site Initiation (Form Control No. **VCCL-0002**).

On-site visits may be considered when, for example, hands-on training or evaluation of site facilities is required. While on site, the Clinical Research Associate (CRA) will follow all local, state, and governmental policies for COVID-19 Risk Mitigation, including social distancing, wearing of PPE, etc. as applicable for the location of the study site.

6.1.2 Interim Monitoring Visits (if applicable):

During the period that this Work Instruction is in effect, Interim Monitoring On-site visits will be kept to a minimum and include only those tasks that the CRA cannot perform remotely (e.g., source document verification, test article reconciliation, etc.).

To ensure data integrity during the conduct of all JJVC studies, clinical study teams will follow the study specific Clinical Monitoring Plan (Form Control No. **VCT-0026**).

While on site, the CRA will follow all local, state, and governmental policies for COVID-19 Risk Mitigation, including social distancing, wearing of PPE, etc. as applicable for the location of the study site.

Title:	Guidelines for COVID-19 Risk Mitigation
Document Type:	Work Instruction
Document Number:	VWI-0081

6.1.3 Study Site Closure:

During the period that this Work Instruction is in effect, the duration of the Study Site Closure Visit will be limited to tasks that the CRA cannot perform remotely (e.g., source document verification, test article final reconciliation and return, etc.).

Title:	Guidelines for COVID-19 Risk Mitigation
Document Type:	Work Instruction
Document Number:	VWI-0081

Revision Number: 1

**AMENDMENT HISTORY**

Version Number	Revision Date (DD/MM/YYYY)	Reasons for Revision
1.0	03 November 2020	Original

**ABBREVIATIONS**

AE	adverse event
CLVA	Contact Lens Visual Acuity
CrI	Credible interval
CRF	case report form
CSR	Clinical Study Report
DMC	Data Monitoring Committee
eCRF	electronic case report form
FDA	Food and Drug Administration
HLHC	High Luminance High Contrast
ICH	International Conference on Harmonization
ITT	Intent-to-Treat
IVRS	interactive voice response system
LOCF	last observation carried forward
PI	principal investigator
SAE	serious adverse event
SAP	Statistical Analysis Plan
SD	standard deviation
VP	Visual Performance

## 1. INTRODUCTION

This statistical analysis plan (SAP) describes the analyses and data presentations for protocol CR-6400 Version 4.0.

This document will serve as the final guidance for all the statistical analysis for this study and will supersede the Statistical Method section in the protocol if there are any discrepancies. Any deviation from the analysis plan will be documented as such in the clinical study report.

## 2. STUDY OBJECTIVES

Primary Objective:

The primary purpose of this study is to demonstrate that the Multifocal Test lens made with senofilcon A material made from the Flexible Manufacturing Platform (FMP), in its final lens design FAL100, FAL101 and FAL102 (low, mid and high ADD respectively) meets the design validation requirements for CLUE overall quality of vision scores, logMAR visual acuity, ocular physiology and lens fit acceptance.

Secondary Objective:

The secondary objective is to evaluate the number of lenses needed to optimize the subject's vision.

## 3. STUDY DESIGN

### 3.1. Overview

The clinical study is a bilateral, single-masked (partial), single-arm, clinical trial. A total of approximately 60 eligible subjects (30 myopes and 30 Hyperopes) will be targeted to complete the study.

The study begins with an initial visit, Visit 1 (Day 0), if a subject is found to meet all eligibility criteria, they will be fit with the study lens, in both eyes; otherwise the subject will be deemed ineligible and classified as a screen failure.

If a subject is dispensed lenses at the initial visit, then two additional visits will be conducted. Visit 2 will occur  $3 \pm 1$  days after Visit 1. At Visit 2 subjects will undergo lens optimization if the subject reports unsatisfactory vision or is unable to obtain 20/30 binocular distance visual acuity with the study lenses. Subjects will return for Visit 3 (Final Evaluation) after  $12 \pm 2$  days. At the final visit, subjects will undergo subjective and objective assessments of vision.

Subjects will be advised to wear the study lenses every day while they are in the study for a minimum of 6 hours per day. The study lens will be replaced at the optimization visit. However, lost or damaged lenses maybe replaced when necessary. Unscheduled visit may be conducted.

### 3.2. Test Articles

Table 1: Test article labels

Test Article	Label
JJV Investigational Multifocal Contact Lens	Test
ACUVUE OASYS® with HYDRACLEAR® PLUS Sphere*	Test
All Test Articles	Total

**\*Note:** The spherical test lens (JJV Investigational Multifocal Contact Lens) is used in the troubleshooting steps only for low ADD subjects who have reported a distance vision complaint.

### 3.3. Targeted Study Population and Sample Size

Approximately 80 subjects will be enrolled to ensure that 60 subjects will complete the study (30 myopes and 30 hyperopes). Enrolled subjects will be habitual wearers of soft contact lenses. All subjects will be at least 40 years of age and not older than 70 years of age at the time of enrolment. Eligible presbyopes will be those that wear an a presbyopic contact lens correction (e.g., reading spectacles over contact lenses, multifocal or monovision contact lenses, etc.) or if not respond positively to at least one symptom on the “Presbyopic Symptoms Questionnaire” (CR-6400 Protocol Version 4.0, Appendix E).

Table 2: Planned Enrollment Strategy by Strata and Site

	Myopes	Hyperopes	Total
Enrolled	40	40	80
Randomized	30	30	60
Number of enrolled per site (min-max) Target	2-6	2-6	

### 3.4. Test Article Allocation and Masking

The study lenses will be worn in a bilateral fashion using a single-arm design. Due to the nature of the design no randomization is required.

This is a single arm study and all subjects will be assigned to the same study lens. Subjects will be unaware of the identity of the investigational product. Investigators and clinical site personnel involved in the data collection will not be masked as to the identity of the investigational product.

Subjects who have had their treatment assignment unmasked are expected to return for all remaining scheduled evaluations. Subjects who are discontinued may be replaced.

### 3.5. Time and Event Schedule

See Appendix 14.1 for details regarding the Time and Events Schedule.

## 4. STUDY ENDPOINTS

Primary Efficacy Endpoints:

### CLUE Overall Quality of Vision

Overall comfort scores will be assessed using the Contact Lens User Experience (CLUE™) questionnaire after approximately 2 weeks of lens wear. CLUE is a validated patient-reported outcomes questionnaire to assess patient-experience attributes of soft, disposable contact lenses (comfort, vision, handling, and packaging) in a contact-lens wearing population in the US, ages 18-65. Derived CLUE™ scores using Item Response Theory (IRT) follow a normal distribution with a population average score of 60 (SD 20), where higher scores indicate a more favorable/positive response with a range of 0-120. A 5-point increase in an average CLUE™ score translates into 10% shift in the distribution of scores for population of soft contact lens wearers.

### Visual Acuity (logMAR)

Multiple assessments of binocular and monocular visual acuity will be made during the study, but the binocular measurements made after approximately 2 weeks of lens wear using high contrast letters in bright illuminance conditions will be the primary endpoint. At distance (4 meters), VA is assessed using ETDRS charts; while near (40 cm) and intermediate (64 cm) assessments will be made using reduced Guillon-Poling charts. Visual acuity will be measured using high and low contrast charts in bright illuminance conditions. [REDACTED]

Primary Safety Endpoints:

### Slit Lamp Findings (SLF)

Slit Lamp Findings (Grade 3 or higher) will be assessed for each subject eye at all study visits (scheduled and unscheduled). SLFs will be evaluated and classified using the FDA Grading scale rating from 0 to 4, where Grade 0 represents the absence of findings and 1 to 4 representing successively worse findings (i.e. Grade 1=trace, Grade 2= mile, Grade 3=moderate and Grade 4= severe). The percentage of eyes with Grade 3 or higher slit lamp findings will be analyzed and will include corneal infiltrates. [REDACTED]

### Unacceptable Lens Fit

Unacceptable lens fit will be assessed at all study visits (scheduled and unscheduled) for each subject eye. Unacceptable fit is a binary response where Y=1 if lens fit is unacceptable and

CR-6400, Statistical Analysis Plan Version 1.0

Y=0 otherwise. Unacceptable fit was defined as unacceptable if any one of the following criteria:

- limbal exposure at primary gaze or with extreme eye movement;
- edge lift;
- excessive movement in primary up gaze;
- insufficient movement in all three of the following conditions: primary gaze, up gaze, and push up test.

Eyes with multiple unacceptable fitting events was counted only once. See CTP-2008 in Appendix H for additional details regarding lens fit assessments.

#### **4.1. Secondary Endpoints**

Summary of lenses needed to fit (optimize) the subject's vision

#### **4.2. Other Endpoints**

- Lens Deposits
- CLUE comfort/handling scores
- GSI Product Performance ratings

### **5. STATISTICAL HYPOTHESES FOR STUDY OBJECTIVES**

#### **5.1. Primary Hypotheses**

All the following co-primary hypotheses must be satisfied in order to meet the study objectives.

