We calculated the required sample size with and without borrowing historical data. To achieve a minimum of 80% power with a 2-sided type I error rate of 5%, the required sample size with no borrowing ($a_0 = 0$) was 120 subjects (240 eyes); while the sample size with borrowing was 60 subjects (120 eyes). The sample calculation in each scenario of borrowing was conducted using a Monte Carlo simulation of 1000 trials of samples of size 120 subjects (240 eyes) were drawn from a multivariate binary distribution assuming a compound symmetric (CS) covariance structure between left and right eye from the same subject. Assuming a true proportion of eyes with grade 3 or higher SLFs of $p=0.014$ and a correlation of $\rho=0.70$ between left and right eyes. The same approach was considered for the proportion of eyes with unacceptable fitting assuming a true proportion of eyes with unacceptable fit of $p=0.01$ and a correlation of $\rho=0.80$ between left and right eyes.

The sample size was mainly driven by safety analysis, the power calculation of the efficacy analysis showed that a sample size of 60 subjects is sufficiently large to test the efficacy hypotheses. No borrowing was considered for the primary efficacy analysis. Table 8 summarize the statistical power of a sample size of 60 subjects (120 eyes) for all endpoints.

Table 10: Power Calculation by Endpoint/Hypothesis Assuming a Sample Size of 60 Subjects

Endpoint	Borrowing	Hypothesis (H_A)	Power (%)
Grade 3 or Higher SLFs	Yes	$p_t < 0.05$	80
Unacceptable lens tit	Yes	$p_t < 0.05$	90
VA Distance	No	$\mu_t < +0.10$	> 99
VA Intermediate	No	$\mu_t < +0.17$	> 99
VA Near	No	$\mu_t < +0.17$	> 99
CLUE Vision (Hyperopes)	No	$\mu_t \geq 32$	99
CLUE Vision (Myopes)	No	$\mu_t \geq 40$	99

The power calculation of the efficacy analyses (CLUE and VA) was conducted using historical data presented in Table 5 above using PROC POWER for one sample means test for equivalence to test each hypothesis.

The plan is to enroll 80 eligible subjects with a target completion of 60 subjects. During the enrollment period, the subject drop-out rate will be closely monitored, if an unexpectedly high

Clinical Study Protocol

Johnson & Johnson Vision Care, Inc.

dropout rate is observed, then the targeted total enrollment number maybe be increased accordingly to ensure that a minimum of 60 subjects complete the study.

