### **Safety Analysis**

Our plan for safety analysis is to incorporate historical individual subject data from the 6 studies using power prior distributions in a Bayesian framework (see section 14.5). The level of influence of historical data on current is determined by a discounting factor  $a_0$  constrained between 0 and 1 ( $0 \leq a_0 \leq 1$ ).  $a_0 = 0$  corresponds to no borrowing of the historical data; while  $a_0 = 1$  corresponds to full borrowing (See section 14.5 for more details). For this study we considered a low level of borrowing ranging by 0.1 and 0.30 based on the manufacturing platform where the historical study lens was made from. Table 7 displays the number of subjects and the degrees of borrowing that will be used in the safety analysis. The approved investigational product will be manufactured from the FMP platform; therefore, the borrowing strength is larger to lenses from the FMP platform. Furthermore, the TAM21 platform is considered equivalent with respect to lens performance and lenses from these platforms are given the same borrowing strength as those from the FMP platform. While all historical studies used the lens in its final design, lenses made from the pilot line are only given a borrowing strength of 10%.

Table 7: Degrees of Borrowing Historical Data by Manufacturing Platform

Manufacturing Platform	Number of Subjects	Level of borrowing ( $a_0$ )
FMP	23	0.3
TAM21	66	0.3
Pilot Line (SCLM, MCLM)	86	0.1

We calculated the required sample size with and without borrowing historical data. To achieve a minimum of 80% power with a 2-sided type I error rate of 5%, the required sample size with no borrowing ( $a_0 = 0$ ) was 120 subjects (240 eyes); while the sample size with borrowing was 60 subjects (120 eyes). The sample calculation in each scenario of borrowing was conducted using a Monte Carlo simulation of 1000 trials of samples of size 120 subjects (240 eyes) were drawn from a multivariate binary distribution assuming a compound symmetric (CS) covariance structure between left and right eye from the same subject. Assuming a true proportion of eyes with grade 3 or higher SLFs of  $p=0.014$  and a correlation of  $\rho=0.70$  between left and right eyes. The same approach was considered for the proportion of eyes with unacceptable fitting assuming a true proportion of eyes with unacceptable fit of  $p=0.01$  and a correlation of  $\rho=0.80$  between left and right eyes.

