The sample size was mainly driven by safety analysis, the power calculation of the efficacy analysis showed that a sample size of 60 subjects is sufficiently large to test the efficacy hypotheses. No borrowing was considered for the primary efficacy analysis. Table 8 summarize the statistical power of a sample size of 60 subjects (120 eyes) for all endpoints.

Table 8: Power calculation by endpoint/hypothesis assuming a sample size of 60 subjects

Endpoint	Borrowing	Hypothesis ( $H_A$ )	Power (%)
Grade 3 or Higher SLFs	Yes	$p_t < 0.05$	80
Unacceptable lens tit	Yes	$p_t < 0.05$	90
VA Distance	No	$\mu_t < +0.10$	> 99
VA Intermediate	No	$\mu_t < +0.17$	> 99
VA Near	No	$\mu_t < +0.17$	> 99
CLUE Vision (Hyperopes)	No	$\mu_t \geq 32$	99
CLUE Vision (Myopes)	No	$\mu_t \geq 40$	99

The power calculation of the efficacy analyses (CLUE and VA) was conducted using historical data presented in Table 5 above using PROC POWER for one sample means test for equivalence to test each hypothesis.

The plan is to enroll 80 eligible subjects with a target completion of 60 subjects. During the enrollment period, the subject drop-out rate will be closely monitored, if an unexpectedly high dropout rate is observed, then the targeted total enrollment number maybe be increased accordingly to ensure that a minimum of 60 subjects complete the study.

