## 8.5. Statistical Significance Level

All planned analysis for this study will be conducted with an overall type I error rate of 5%.

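### The 80% power target holds for each endpoint separately; with all seven co-primaries required, Table 8 puts the power to meet the objective at no more than 80%, and about 71% if the endpoints are independent.

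*SAP*

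**What the plan says.** - **Success rule.** SAP section 5.1 (and protocol section 2.3): "All the following co-primary hypotheses must be satisfied in order to meet the study objectives". The seven are CLUE vision in myopes, CLUE vision in hyperopes, logMAR acuity at distance, intermediate and near, slit-lamp findings of Grade 3 or higher, and unacceptable lens fit. The secondary hypothesis is tested only if all seven are met.
- **What the study is powered for.** SAP section 8.4 and protocol section 14.2 open by saying that the study was powered to show that the lens meets its design validation requirements. The wording closely follows the primary objective in SAP section 2.
- **Sizing.** Under the Safety Analysis heading of SAP section 8.4: "To achieve a minimum of 80% power with a 2-sided type I error rate of 5%, the required sample size with no borrowing" was 120 subjects, "while the sample size with borrowing was 60 subjects (120 eyes").
- **Power reported.** SAP Table 8 (protocol Table 10) is captioned "Power calculation by endpoint/hypothesis assuming a sample size of 60 subjects". Its rows are slit-lamp 80%, lens fit 90%, each of the three acuity tests above 99%, and each of the two CLUE tests 99%.
- **Type I error.** SAP section 8.5: "All planned analysis for this study will be conducted with an overall type I error rate of 5"%.

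Neither document states a power for meeting all seven hypotheses, or how the seven tests depend on one another.

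**The concern.** When every test must succeed, the power that matters for the objective is the probability that all seven succeed in the same trial. That probability cannot exceed the smallest single power. It falls below that value unless every trial that passes the weakest test also passes the other six. The plan declares the study powered for the objective and then supports this with seven separate powers, the smallest of which equals the stated minimum.

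Someone deciding whether 60 subjects are enough could take 80% as the chance that a lens performing as assumed will meet the objective. On the plan's own figures, that is the best case. The same joint power also caps the chance of any secondary claim, because the secondary test is conditional on all the primaries. The only provision in section 8.4 for raising enrolment is an unexpectedly high dropout rate, so nothing else in the plan addresses the gap.

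There is no type I error problem. An all-must-pass rule needs no adjustment of alpha; its cost falls on power.

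**Working it through.** **Inputs (SAP Table 8, 60 subjects).** Slit-lamp 0.80; fit 0.90; CLUE hyperopes 0.99; CLUE myopes 0.99; three acuity tests each above 0.99. The dependence between tests is not given, so a range is shown.

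**Step 1. Reproduce the efficacy rows.** I used a one-sample t test, one-sided 0.025, with the means and SDs of SAP Table 5 and the common acuity SD of 0.11. The noncentrality is (distance from threshold) / (SD / sqrt(n)).

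| Row | n | Noncentrality | Power |
|---|---|---|---|
| Distance acuity | 60 | 0.177 / (0.11/sqrt(60)) = 12.5 | about 100% |
| Intermediate acuity | 60 | 0.224 / (0.11/sqrt(60)) = 15.8 | about 100% |
| Near acuity | 60 | 0.093 / (0.11/sqrt(60)) = 6.55 | 99.9996% |
| CLUE hyperopes | 30 | 15.71 / (17.514/sqrt(30)) = 4.91 | 99.7% |
| CLUE myopes | 30 | 16.46 / (19.227/sqrt(30)) = 4.69 | 99.5% |

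These agree with Table 8. The safety rows are taken from the table as printed; recomputing them is discussed under the objection.

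**Step 2. Joint power if the endpoints are independent.**

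- Table figures, acuity taken as 1: 0.80 x 0.90 x 0.99 x 0.99 = 0.706.
- Acuity taken as only 0.99 each: 0.706 x 0.99^3 = 0.685.
- Reproduced CLUE powers, acuity as 1: 0.80 x 0.90 x 0.997 x 0.995 = 0.714.
- The two safety rows alone: 0.80 x 0.90 = 0.72.

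**Step 3. Limits under any dependence.**

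- Upper limit, the smallest single power: 0.80.
- Lower limit, 1 minus the sum of the failure probabilities: 1 - (0.20 + 0.10 + 0.01 + 0.01) = 0.68. With the acuity rows at 0.99 each, a further 0.03 comes off, giving 0.65.

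**Step 4. Positive dependence.** This is an illustrative Gaussian copula on the slit-lamp, fit and two CLUE rows, with one common correlation and acuity taken as 1. The correlations are assumed.

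| Correlation | Joint power |
|---|---|
| 0 | 0.71 |
| 0.1 | 0.71 |
| 0.3 | 0.73 |
| 0.5 | 0.75 |
| 0.8 | 0.78 |

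**Step 5. What 80% joint power would need.** Under independence with each CLUE row at 0.99, both safety tests would need a power of sqrt(0.80 / 0.99^2) = 0.903.

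**The case against.** **The plan does not claim 80% for the joint objective.** The sentence with the 80% minimum sits under the Safety Analysis heading, and the Table 8 caption says that the powers are by endpoint or hypothesis. This stands. A reader might infer that Table 8 contains an error or that the plan asserts 80% joint power; the text does neither. What remains is that section 8.4 says the study is powered for the objective and never gives the power that the section 5.1 rule implies.

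**A flat figure of about 70% is not in the table.** This also stands. The 71% needs independence, which neither document states. Without that assumption, the table supports only the range in Step 3. The low end of that range is itself cautious, since it reads three entries above 99% as exactly 99% when they recompute to essentially 100%.

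**The safety tests may have more than 60 subjects.** They use the safety population, which includes dispensed subjects who drop out, and 80 are to be enrolled. This is fair, but the documents do not say how many such subjects to expect, and Table 8 is expressly for 60.

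**A harsher reading is tempting.** With the Beta(0.5, 0.5) prior in the SAP code and the 0.975 rule, the slit-lamp row at 60 subjects recomputes to about 0.50 to 0.75 and the fit row to about 0.85. Multiplying through gives 0.502 x 0.852 x 0.997 x 0.995 = 0.42, up to 0.745 x 0.852 x 0.997 x 0.995 = 0.63. The documents do not support presenting this as the trial's power. The slit-lamp result turns on how the five historical events divide between platforms borrowed at 0.3 and at 0.1, which is not stated. The prior used in the sizing simulation is not stated either. With a 0.95 criterion, or with a prior close to zero weight, the same calculation gives about 0.75 to 0.85 for slit-lamp and 0.91 for fit, consistent with the printed 80% and 90%. Whether those two rows are right is a separate question.

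**Conclusion.** The point holds as a missing figure that bears on the sizing claim. On Table 8's own entries, the power to meet the primary objective with 60 subjects is at most 80%. It is about 71% if the seven tests are independent, and about 65% to 68% at the lowest under any dependence. For a lens performing exactly as assumed, the chance of missing the objective is therefore at least 20%, and about 29% under independence.

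The upper limit rests only on the printed 80% and the all-must-pass rule. The 71% rests on independence and on the safety rows being correct as printed. The two safety endpoints account for nearly all the loss; the efficacy tests contribute very little.

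The finding does not show that a Table 8 entry is wrong, and it does not affect type I error or the validity of the analysis.

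**What to change.** In SAP section 8.4 and protocol section 14.2:

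1. State that the 80% minimum applies to each endpoint separately.
2. Add one sentence giving the power to meet all seven hypotheses at 60 subjects: about 71% assuming independent endpoints, and at most 80%.
3. Preferably, replace that approximation with a simulated joint power, using the Beta(0.5, 0.5) prior in the SAP code, the 0.975 success rule and the actual historical data, and state the dependence assumed between endpoints. The sponsor holds the historical subject-level data, so the same simulation would also settle the two safety rows.

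Items 1 and 2 cost a sentence or two and a less favourable headline figure; item 3 costs a modest extension of the existing simulation. None of them adds subjects or changes the analysis or the decision rules.
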